1.0 Background & Rationale

Electroencephalography (EEG) was first described in 1875 in dogs and apes.¹ The technology was shortly after applied to humans and within 10 years the changes to the EEG tracing was studied when certain sedatives drugs were administered.¹ Over the last several decades EEG based monitors have been developed with the hopes of aiding anesthesiologists at evaluating the “depth” of a patient’s anesthetic while under general anesthesia. Currently, typical anesthesia practice is to measure and adjust depth of a general anesthetic based on the medications administered and hemodynamic parameters of the patient, potentially exposing high risk patients to un-needed excessive depths of anesthesia which can potentially result in adverse post-operative outcomes.^{2,3}

The use of intraoperative EEG monitoring to guide the depth of an anesthetic seems to have the potential to reduce the total dose of anesthetic required. Use of the EEG based monitor called the Bispectral Index Monitor (BIS Monitor) in an older study was shown to reduce sedative use and total cost in ICU patients who were receiving intravenous infusions of sedatives and neuromuscular blockers.⁴ And recently, the BIS monitor was used in a large randomized control study in order to investigate whether providing an anesthetic guided by an EEG based monitoring device in individuals at high risk for postoperative delirium would significantly reduce postoperative delirium. While the primary results reported a negative results, the study did have other interesting findings – most notably a significant reduction in the dosage of volatile anesthetic (the primary anesthetic agent used in general anesthetic procedures). Furthermore, the study showed using a protocolized adjustment in anesthetic depth using an EEG based monitoring system for guidance in human subjects resulted in no significant change in adverse outcomes in a large trial of patients in this population⁵

The Masimo Sedline Brain Function Monitor (SedLine), is an EEG based monitoring device that is approved by the Food and Drug Administration for monitoring of brain function under anesthesia. This new generation device provides processed EEG information (as the BIS monitor does) as well as raw EEG waveforms and a Density Spectral Array (DSA) display – providing information of the power of the EEG signal over a spectrum of frequencies. This additional

information allows the anesthesiologist to evaluate the depth and appropriateness of the anesthetic in detail.⁶

We hypothesize that the use of a Sedline processed EEG monitor (using a protocolized adjustment in anesthetic depth using this EEG monitoring device) will allow anesthesiologists to reduce the doses of anesthetic drugs during general anesthesia in patients 65 or older (resulting in less exposure of anesthetic medications to a high-risk patient population as well as a potential reduction in cost). In addition, an added benefit of safely reducing the amount of volatile anesthetic used in everyday anesthesia practice may prove to also be helpful to environment and cut down on their contribution to ozone layer depletion.⁷

We plan to investigate this hypothesis in a study in which we will randomize patients to either anesthetic drug doses guided by Sedline processed EEG characteristics or standard anesthesia care. We plan to evaluate the hypothesis that SedLine monitoring reduces anesthetic drug doses.

Of note, we have recently completed a pilot study with a similar study design and have confirmed we have the capabilities and resources to conduct this study.

2.0 Objective(s)

2.1 Primary Objective

The primary objective of this study will be to determine whether an anesthetic guided by the Sedline EEG based monitor will reduce the total dosage of anesthetic under general anesthetics in this population (patients 65 or older).

3.0 Outcome Measures/Endpoints

3.1 Primary Outcome Measures

The primary outcome measured will be the total average percent of volatile anesthetic (sevoflurane) utilized while subjects are under anesthesia (maintenance phase). The time considered “maintenance phase” under general anesthesia will be measured starting 5 minutes after the induction agents are administered and measurements will stop following

administration of neuromuscular blocker reversal drugs. Data will be collected from computerized anesthetic records.

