3.2 Secondary Outcome Measures

The secondary outcomes measured will be the total dosage of hypnotic agents administered while in the maintenance phase of anesthesia. These agents include: midazolam, lorazepam, diazepam, fentanyl, sufentanil, ketamine, propofol, morphine, and hydromorphone. Additional secondary outcomes measured will include episodes of hypotension (this will be defined as an episode of mean arterial pressure of <65 mmHg), total dosage of vasopressors (such as phenylephrine, ephedrine, vasopressin, or norepinephrine), and the occurrence of EEG isoelectricity, or burst suppression. SedLine images will be recorded for both groups in order to compare rates and duration of burst suppression events. Of note, if the patient has a functioning arterial line in place, we will use measurements from this in preference to a non-invasive blood pressure cuff).

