5.0 Study Design

[figure not shown]
- Prior to study commencement, select anesthesiologists from the Indiana University Health University Hospital Anesthesia Group will be trained on usage and interpretation of the Sedline. Training for this group of providers will include a PowerPoint presentation recording presented by [name] to aid in interpretation of the Sedline data. Representatives from the study will also be available as needed to answer questions as they arise. They will also be given certain guidelines for anesthetic administration based on the processed EEG findings. These will include the following:
 - Usage of sevoflurane as the primary anesthetic agent
 - Reducing sevoflurane dosage if the EEG indicates signs of burst suppression (excessive anesthetic depth), if the PSI on the Sedline reads less than 25, or if hypotension is occurring and the anesthesia provider believes that depth of anesthesia may be a contributing factor.
 - Increasing sevoflurane dosage if the EEG pattern is not consistent with general anesthesia (not enough depth of anesthetic).
- We anticipate 5-10 anesthesiologists being included in this group. Given that this group of anesthesiologists will be assigned to both groups (study and control), the size of the groups, and the instructions regarding the maintenance phase of anesthesia, diazepam, and dexmedetomidine we anticipate the difference in practice patterns between providers will not affect the data. We will discourage the use of nitrous oxide as well as IV anesthetics including midazolam. In the control group, the anesthesiologist will be asked to provide the anesthetic as he or she would under normal care with the exception of avoidance of nitrous oxide and IV anesthetics during the maintenance phase of anesthesia. We anticipate

that the surgical procedures included in this study will be similar enough that the type of surgical procedure will not affect anesthetic dosing.

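### Does an objective about total anesthetic dosage need a cumulative sevoflurane endpoint instead of an average percent?

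*Combined protocol and SAP*

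**What the plan says.** Objective 2.1, the only objective in the protocol, asks whether Sedline guidance "will reduce the total dosage of anesthetic under general anesthetics in this population". The rationale in section 1.0 speaks of "resulting in less exposure of anesthetic medications to a high-risk patient population" and of "safely reducing the amount of volatile anesthetic used in everyday anesthesia practice".

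The endpoint in section 3.1 is narrower: "The primary outcome measured will be the total average percent of volatile anesthetic (sevoflurane) utilized while subjects are under anesthesia (maintenance phase". The window opens 5 minutes after the induction agents and closes at neuromuscular blocker reversal, so its length differs between patients. On the source, the section says "Data will be collected from computerized anesthetic records". It does not say whether the mean is time-weighted or which recorded percent is meant.

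The outcomes stated as totals are in section 3.2: "The secondary outcomes measured will be the total dosage of hypnotic agents administered while in the maintenance phase of anesthesia", followed by a list of agents without sevoflurane, and "total dosage of vasopressors (such as phenylephrine, ephedrine, vasopressin, or norepinephrine".

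Section 5.0 uses the word dosage for the level being titrated, as in "Reducing sevoflurane dosage if the EEG indicates signs of burst suppression". Section 12.0 repeats the average percent as the primary outcome and bases the sample size on it. It names duration as an optional fixed effect and plans summaries of all data by treatment group.

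**The concern.** A lower average concentration is not the same thing as a smaller total. If the study arm had longer maintenance phases, its patients could receive as much sevoflurane as controls, or more, at a lower average percent. The protocol makes sevoflurane the primary agent, yet no listed outcome totals it, and duration by arm is not an outcome. Read strictly, the trial could succeed on its primary endpoint without having measured the quantity in its objective, and a statement about total exposure would rest on an unchecked step. The phrase used for the endpoint adds to the doubt, because it puts total and average side by side without explanation.

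**Working it through.** **Inputs.** From section 12.0: coefficient of variation (CV) 0.15 for the average percent, ratio of means 0.90, two-sided 5% level, 90% power, 44 evaluable per group, dropout up to 20%, 55 enrolled per group, and a test for the ratio of two means. The documents give no CV for duration, so 0.2, 0.3 and 0.6 are assumed here, with duration log-normal and independent of arm and of average percent.

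**1. The plan's own figure, for the average percent.**
- Log-scale SD = sqrt(ln(1 + 0.15²)) = 0.1492
- Effect = |ln 0.90| = 0.1054
- SE = 0.1492 × sqrt(2/44) = 0.0318
- Noncentrality = 0.1054 / 0.0318 = 3.31 on 2 × 44 − 2 = 86 degrees of freedom, giving power 0.906. The smallest n per group reaching 90% is 44.
- Enrolment = 44 / 0.80 = 55 per group, 110 in all
- Expected 95% CI at a true ratio of 0.90, with t = 1.988: 0.90 × exp(∓1.988 × 0.0318) = 0.845 to 0.959

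The plan's sample size is correct for the endpoint it defines.

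**2. From average to total.** For each patient, percent-hours = average percent × duration. On the log scale the arm ratios therefore multiply: ratio of totals = ratio of averages × ratio of durations. With equal durations, 0.90 × 1 = 0.90, so the total falls by the same 10%. The effect on the total disappears only if 0.90 × r = 1, that is r = 1 / 0.90 = 1.11.

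**3. Percent-hours at 44 per group, true ratio 0.90, unadjusted.** Log-scale SD = sqrt(ln(1.0225) + ln(1 + CV²)), and SE = SD × sqrt(2/44).

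| Assumed duration CV | Log SD | SE | 95% CI | Power | n per group for 90% power |
|---|---|---|---|---|---|
| 0.2 | 0.248 | 0.053 | 0.810 to 1.000 | 0.504 | 118 |
| 0.3 | 0.329 | 0.070 | 0.783 to 1.035 | 0.317 | 207 |
| 0.6 | 0.574 | 0.122 | 0.706 to 1.148 | 0.136 | 626 |

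**4. Duration by arm when the true ratio is 1.** The 95% CI is exp(∓1.988 × sqrt(ln(1 + CV²)) × sqrt(2/44)): 0.919 to 1.088, 0.883 to 1.132 and 0.791 to 1.265 for the three CVs. At the two larger CVs, chance alone could move the observed ratio past 1.11. That is noise from case length. It would enter an observed total and leaves the average free of it, which is a reason to prefer the average as primary.

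**5. Effect on the planned primary analysis.** None. Sections 3.1 and 12.0 both specify an average percent, and the word total in Objective 2.1 does not enter the computation.

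**The case for a change.** The strongest case for a change is that section 3.2 uses the same words, total dosage, for quantities that really are totals, so Objective 2.1 can hardly mean a level. Randomization balances duration only in expectation, and duration is not a listed outcome. The averaging rule and the choice among end-tidal, inspired or dialed values are open, while section 5.0 says the investigators who collect outcomes cannot be blinded. Aligning the wording and adding percent-hours would cost no patients.

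Part of this stands. The wording is loose, no outcome totals sevoflurane, and a claim about total exposure would go beyond what is listed. It does not carry further, for four reasons.

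- **Wording.** Section 5.0 uses dosage for the titrated level, and the average fits that use. The phrases about exposure and amount belong to the rationale and are not objectives.
- **Duration.** Section 12.0 names it as a possible covariate and plans summaries of all data by group. This coverage is partial, because the covariate is optional and may mean length of surgery. If duration is collected, the check in step 2 is available.
- **Averaging details.** A mean over a stated window is ordinarily taken over time, and equally spaced readings make simple and time-weighted means the same. One recorded percent, used for every patient in both arms, keeps the randomized comparison valid. The lack of blinding is a reason to fix that choice once for all patients, which is routine when the variable is defined.
- **The added secondary.** Its interval reaches about 1 or crosses it at every assumed CV, and percent-hours is not volume consumed, so it would not settle the cost or environmental argument either. Narrowing the sole objective to sevoflurane concentration would also leave the hypnotic-agent totals in section 3.2 without an objective above them.

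**Conclusion.** The mismatch in wording is real, but it does not call for a change. The endpoint is coherent, stated consistently where it is defined and analysed, and correctly sized: 44 per group, power 0.906, expected 95% CI about 0.84 to 0.96 at a true ratio of 0.90. A lower average implies a lower expected total provided that monitoring does not lengthen the maintenance phase and the proportional reduction does not depend on duration. The documents give no reason to doubt either condition, and about 11% more time in the study arm would be needed to cancel a 10% reduction.

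Percent-hours as primary would need roughly 118 to 626 per group. As an unadjusted secondary it would have power of about 0.50 to 0.14. Both ranges rest on assumed duration CVs of 0.2 to 0.6 and on independence. The conclusion on the primary comparison does not depend on those assumptions. What remains is one loose word in the objective and some detail on how the average is taken, which competent analysts supply without altering the design or the result.

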3.2 Secondary Outcome Measures

The secondary outcomes measured will be the total dosage of hypnotic agents administered while in the maintenance phase of anesthesia. These agents include: midazolam, lorazepam, diazepam, fentanyl, sufentanil, ketamine, propofol, morphine, and hydromorphone. Additional secondary outcomes measured will include episodes of hypotension (this will be defined as an episode of mean arterial pressure of <65 mmHg), total dosage of vasopressors (such as phenylephrine, ephedrine, vasopressin, or norepinephrine), and the occurrence of EEG isoelectricity, or burst suppression. SedLine images will be recorded for both groups in order to compare rates and duration of burst suppression events. Of note, if the patient has a functioning arterial line in place, we will use measurements from this in preference to a non-invasive blood pressure cuff).

4.0 Eligibility Criteria

4.1 Inclusion Criteria

- Patients undergoing a scheduled surgery (laparotomy, hepatobiliary surgery, gynecologic surgery, and/or urologic surgery procedures) at Indiana University Health University Hospital that is expected to have at least a 3 day post-operative hospital stay.
- ASA class 1, 2, 3, or 4.
- Age 65 years or older.
- Male or Female
- Surgical procedure requiring general anesthesia.

4.2 Exclusion Criteria

- Any previous diagnosis of dementia or other cognitive impairment.
- Any patient undergoing emergency surgery.
- Any patient undergoing surgery who is currently an inpatient.
- Patient refusal to participate in study.

- Any patient undergoing surgery that would prevent placement of the Sedline monitor leads (for example – surgery on the patient’s forehead/scalp).
- Any physical, mental, or medical conditions which, in the opinion of the investigators, may confound the ability to assess the patient for delirium in the post-operative period.

5.0 Study Design

[figure not shown]
- Prior to study commencement, select anesthesiologists from the Indiana University Health University Hospital Anesthesia Group will be trained on usage and interpretation of the Sedline. Training for this group of providers will include a PowerPoint presentation recording presented by [name] to aid in interpretation of the Sedline data. Representatives from the study will also be available as needed to answer questions as they arise. They will also be given certain guidelines for anesthetic administration based on the processed EEG findings. These will include the following:
 - Usage of sevoflurane as the primary anesthetic agent
 - Reducing sevoflurane dosage if the EEG indicates signs of burst suppression (excessive anesthetic depth), if the PSI on the Sedline reads less than 25, or if hypotension is occurring and the anesthesia provider believes that depth of anesthesia may be a contributing factor.
 - Increasing sevoflurane dosage if the EEG pattern is not consistent with general anesthesia (not enough depth of anesthetic).
- We anticipate 5-10 anesthesiologists being included in this group. Given that this group of anesthesiologists will be assigned to both groups (study and control), the size of the groups, and the instructions regarding the maintenance phase of anesthesia, diazepam, and dexmedetomidine we anticipate the difference in practice patterns between providers will not affect the data. We will discourage the use of nitrous oxide as well as IV anesthetics including midazolam. In the control group, the anesthesiologist will be asked to provide the anesthetic as he or she would under normal care with the exception of avoidance of nitrous oxide and IV anesthetics during the maintenance phase of anesthesia. We anticipate

that the surgical procedures included in this study will be similar enough that the type of surgical procedure will not affect anesthetic dosing.

We will identify subjects who meet inclusion/exclusion criteria on the day of surgery. Following explanation of the study and completion of informed consent, the patient will be randomized into 1 of 2 groups – study group or control group. We plan to use block randomization to keep the groups relatively balanced throughout enrollment. The patient will then be taken to the operating room in normal fashion. Prior to the induction of anesthesia, the Sedline monitor will be placed on the patient's head to ensure the monitor is working properly. For those in the study group, the monitor will be in full view of the anesthesiologist administering the anesthetic. For those in the control group, an apparatus will be placed over the monitor will not be in view of the anesthesiologist. The monitor will still be processing and recording EEGs for both groups. The patient will then be placed under anesthesia and surgery will commence. While under anesthesia, images of the display screen of the Sedline will be collected for later evaluation. Once the surgery is complete, the patient will have the monitor removed and image capture of the display will be stopped prior to exiting the operating room.

Following finalization of the anesthetic record by the staff anesthesiologist, the primary and secondary outcomes will be collected by investigators. The images of the Sedline EEG monitor will also be reviewed by investigators to ensure that appropriate depth of anesthetic was utilized throughout the maintenance phase of anesthesia in the study group. Blinding of the study investigators will not be possible due to the manner in which images of the Sedline readings are collected (it will be readily apparent on the images whether the SedLine data was readily available or concealed from the anesthesia team).

Prior to Enrollment

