12.0 Statistical Considerations

Primary outcome: total average percent of volatile anesthetic (sevoflurane) utilized while subjects are under anesthesia.

Secondary outcomes: total dosage of hypnotic and opioid agents administered while in the maintenance phase of anesthesia. These agents include midazolam, lorazepam, diazepam, fentanyl, sufentanil, ketamine, propofol, morphine, and hydromorphone during the maintenance phase of anesthesia. Additional secondary outcomes measured will include episodes of hypotension, episodes of burst suppression, and total dosage of vasopressors and hypnotic agents.

Statistical analysis will be performed using a standard statistical program (SAS or Stata). All data will be summarized (either means and standard deviations or medians and quartiles for continuous variables; frequencies and percentages for categorical variables) by treatment group. Demographic data will be compared between the two groups using t-test or Wilcoxon rank sum test as appropriate for continuous variables, and chi-square tests or Fisher's exact test for categorical variables as appropriate. The primary outcome, total average percent of volatile anesthetic (sevoflurane) utilized along with secondary outcomes of total dosage of hypnotic agents administered, will be compared between the two groups using t-test or Wilcoxon rank sum test as appropriate. To account for the possible effects of covariates age, sex, and BMI and anesthesiologist, a mixed model with a random effect for anesthesiologists will be employed. Here we could treat surgery type and duration as fixed effects if needed. The secondary outcome of episodes of hypotension which will be compared using chi-square tests or Fisher's exact test for the occurrence of hypotension. Distributions of the continuous variables will be examined, and a transformation of the data (e.g. natural logarithm) or nonparametric tests will be used as necessary. A 5% significance level will be used for all comparisons.

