From a similar study using an outcome (minimum alveolar concentration or MAC) comparable to ours we were able to estimate a coefficient of variation for total average percent of volatile anesthetic to be 0.15.⁴ Working with a feasible sample size of 44 per group and using a power of 90%, 5% significance level, and employing a two-sided test, the study will be able to detect a reduction of 10% in for total average percent of volatile anesthetic between the two groups. Assuming a dropout rate of up to 20%, we will enroll up to 55 patients per group for this study. Here we used a “Tests for the Ratio of Two Means” using sample size software PASS 2019.

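### Cheap precision gain: record any planned neuraxial or regional block before allocation and prespecify it as a covariate for the sevoflurane outcome

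*Combined protocol and SAP*

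**What the plan says.** The primary outcome in Section 3.1 is the "total average percent of volatile anesthetic (sevoflurane) utilized while subjects are under anesthesia (maintenance phase"), taken from the computerized anesthetic record.

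Section 5.0 makes sevoflurane the primary agent and discourages nitrous oxide and IV anesthetics. The control-group anesthesiologist otherwise gives usual care, "with the exception of avoidance of nitrous oxide and IV anesthetics during the maintenance phase of anesthesia". The same section anticipates "that the surgical procedures included in this study will be similar enough that the type of surgical procedure will not affect anesthetic dosing".

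On eligibility, Section 4.1 asks for a "Surgical procedure requiring general anesthesia" and lists laparotomy, hepatobiliary, gynecologic and urologic operations. Nothing in Sections 4.1 or 4.2 addresses a block given alongside general anesthesia.

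On analysis, Section 12.0 says: "To account for the possible effects of covariates age, sex, and BMI and anesthesiologist, a mixed model with a random effect for anesthesiologists" will be used. Its next sentence allows surgery type and duration as fixed effects if needed. Occurrence of hypotension is compared by chi-square or Fisher's exact test, without adjustment. Section 5.0 plans block randomization (allocation blocks) and names no stratification factor.

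No readable section mentions an epidural, spinal, neuraxial or regional technique. The drug list in Section 3.2 covers hypnotics and opioids, with no local anesthetic and no technique.

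**The concern.** The plan limits some co-administered anesthetics and leaves block to the provider's normal care. That a working block can lower volatile requirement and blood pressure is general clinical knowledge; the documents do not say so. If it holds here, and if some patients have a block and others do not, block status is a two-level source of spread in average sevoflurane percent, and also in the hypotension and vasopressor outcomes. No named analysis term removes it.

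What is at stake is precision. Unexplained spread widens the confidence interval for the sevoflurane ratio and, depending on what the planning CV already contains, may lower power below the stated 90%.

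**Working it through.** **Inputs from Section 12.0.** The plan takes the "coefficient of variation for total average percent of volatile anesthetic to be 0.15", a 10% reduction, and a "sample size of 44 per group and using a power of 90%, 5% significance level, and employing a two-sided test". The method is a test for the ratio of two means. Enrollment is up to 55 per group for dropout of up to 20%.

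**Step 1: reproduce the plan's figure.**
- Log-scale variance: ln(1 + 0.15²) = 0.02225, so SD = 0.1492.
- Effect: |ln 0.90| = 0.1054.
- Noncentrality at 44 per group: 0.1054 / (0.1492 × √(2/44)) = 3.31 on 86 degrees of freedom.
- The smallest n for 90% power by noncentral t is 44 per group, with power 0.906. Dropout: 44 / 0.80 = 55.

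The stated sample size is correct on its own inputs.

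**Step 2: variance from block.** The documents give neither the share of patients with a block (p) nor the proportional reduction in sevoflurane (d). I assume p = 0.20 to 0.50 and d = 0.10 to 0.20. On the log scale, block then contributes p(1 − p)[ln(1 − d)]²:
- p = 0.20, d = 0.10: 0.16 × 0.01110 = 0.00178, which is 8% of 0.02225.
- p = 0.40, d = 0.20: 0.24 × 0.04979 = 0.01195, or 54%.
- p = 0.50, d = 0.20: 0.25 × 0.04979 = 0.01245, or 56%.

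**Step 3: two readings of the CV.** The CV of 0.15 comes from another study, and the documents do not say whether its patients had blocks. Case A adds the block variance to 0.02225. Case B takes it as already inside.

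| p, d | A: total CV | A: unadjusted power, 44 per group | A: unadjusted power, 55 per group | B: residual CV after full adjustment | B: adjusted power, 44 per group |
|---|---|---|---|---|---|
| 0.20, 0.10 | 0.156 | 0.883 | 0.942 | 0.144 | 0.927 |
| 0.40, 0.20 | 0.187 | 0.752 | 0.842 | 0.102 | 0.998 |
| 0.50, 0.20 | 0.188 | 0.746 | 0.836 | 0.099 | 0.998 |

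In case A, full adjustment at 44 per group returns power to about 0.906. In case B, unadjusted power is already 0.906.

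**Step 4: imperfect capture.** A yes/no field for planned block will not explain all of the variance. If it explained half of it in the worst row of case A, the residual variance would be 0.02225 + 0.01245/2 = 0.02848, and power 0.825 rather than 0.906.

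**The case against.** The strongest reply is that this is one more optional covariate. Many prognostic factors are absent from the model, and leaving one out does not invalidate a randomized comparison. That stands, and it is why the point is an improvement and not an error.

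Several further limits also stand:
- Surgery type, duration and anesthesiologist are available to the model and may predict block use, so they could absorb part of the variance in the sevoflurane outcome. They do nothing for the unadjusted hypotension test.
- The anesthetic record is already the data source and may well show block use. What is missing is a named field and a named covariate.
- Section 5.0 gives no reason for discouraging nitrous oxide and IV anesthetics, so the plan cannot be charged with breaking a stated principle.
- The primary outcome is collected during surgery. If dropout is well below 20%, the spare enrollment recovers much of any lost power.

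Two stronger readings are tempting. A reader might infer that the trial is underpowered. The documents do not support that: every power below 90% above needs an assumed block frequency, an assumed effect, and a planning CV that excludes both. A reader might also infer bias from unequal block use between arms. Randomization protects against systematic imbalance in blocks planned beforehand. Chance imbalance does occur: at p = 0.40 the arm difference in block share has SD √(2 × 0.4 × 0.6/44) = 0.104, and with d = 0.20 one SD moves the ratio by about 2.3%. But that is ordinary sampling error, already in the unadjusted standard error, and must not be counted as a second harm.

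**Conclusion.** The point holds as a low-cost precision improvement, with low confidence about its size. Block is neither named as a study variable nor adjusted for. The sample-size arithmetic is sound and no bias is shown.

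Under the assumed ranges, the outcome turns on what the CV contains. If block variance is additional, unadjusted power runs from about 88% down to 75% at 44 per group. If it is already included, planned power holds and adjustment only adds to it. The full-adjustment figures are upper limits, because planned block predicts actual block imperfectly and other model terms may share the variance. If blocks are rare in these operations, the gain is close to nil.

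**What to change.** 1. Add one yes/no field, completed before the allocation is released: is a neuraxial or regional block planned for this operation?
2. Prespecify that field as a fixed effect in the mixed model for average sevoflurane percent.
3. Optionally, add a Cochran-Mantel-Haenszel analysis of hypotension stratified by planned block.

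Use the plan recorded before randomization, not the block actually given. Under Section 5.0 the patient is randomized before going to the operating room and the anesthesiologist can tell the arm from the monitor. Actual use could therefore follow allocation and would be a post-randomization variable.

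The cost is one case-report field and one degree of freedom (at 44 per group, 86 becomes 85, with no visible change in power). The downside is little return if blocks are uncommon. No rule on whether or when to use a block is proposed.
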